7.5 Follow-up

The day of the valve implant procedure will be considered Day 0 and will be used to schedule all subsequent visits and calculate visit windows. Six months is defined as 180 days; one year is defined as 365 days.

7.5.1 30 days

The following assessments will be conducted at 30 days post-procedure (+ 14 days):

- Medications: Antithrombotics, antiarrhythmics, heart failure medications and antibiotics only

- NYHA Functional Class
- SF-36 health survey
- 12-lead ECG
- TTE
- Gated CTA: Must be performed after the valve implant procedure but prior to the end of the 30 days follow up period
- CXR
- Adverse events assessment

7.5.2 6 months

The following assessments will be conducted at 6 months post-procedure (+ 14 days):

- Medications: Antithrombotics, antiarrhythmics, heart failure medications and antibiotics only
- NYHA Functional Class
- 12-lead ECG
- TTE
- Fluoroscopy
- Adverse events assessment

7.5.3 12 months

The following assessments will be conducted at 12 months post-procedure (+ 30 days):

- Medications: Antithrombotics, antiarrhythmics, heart failure medications and antibiotics only
- NYHA Functional Class
- SF-36 health survey
- TTE
- cMRI
- Fluoroscopy
- Adverse events assessment

7.5.4 Years 2 through 5, 7 and 10

The following assessments will be conducted at years 2 through 5, 7 and 10 (+ 45 days):

- Medications: Antithrombotics, antiarrhythmics, heart failure medications and antibiotics only
- NYHA Functional Class
- TTE

- CXR or fluoroscopy. For subjects with a previously identified device fracture, fluoroscopy must be performed.
- Gated CTA – at years 5 and 10 only
- Adverse events assessment

7.5.5 Years 6, 8 and 9

The following assessments will be conducted by telephone or office visit at years 6, 8 and 9 (+ 45 days):

- Medications: Antithrombotics, antiarrhythmics, heart failure medications and antibiotics only
- Adverse events assessment

7.6 Imaging Assessments

Imaging performed during the course of the study (TTE, CTA, cMRI, ICE, CXR, fluoroscopy) should follow the applicable Core Lab Manual of Operations.

If CXR reveals potential device fracture, fluoroscopy should be completed for confirmation. If another radiographic assessment (CT, fluoroscopy) has been performed by which fracture can be assessed, then CXR does not need to be performed.

7.7 Quality of Life Questionnaires

QoL will be measured through the following standard survey:

- The SF-36 is a generic health status instrument and rating scale that allows mapping of health status to population-level utility weights. This is an important metric for cost-effectiveness analysis.

Study sites will be provided with paper QoL questionnaires. Questionnaires will be IRB/EC-approved prior to use. Study site personnel will administer questionnaires to subjects at the required time points. Study sites should retain the completed questionnaire in the subjects' medical record.

An overview of study procedures is summarized in the Schedule of Events in **Table 3**.

Table 3: Schedule of Events

| | Screening/ Baseline | Procedure | Discharge | Follow-up | | | | |
|--|------------------------|-----------|----------------|-----------------------|------------------------|-------------------------|---------------------------------|---|
| | | | | 30 Day (+ 14 days) | 6 Month (+ 14 days) | 12 Month (+ 30 days) | 2-5, 7, 10 Years (+ 45 days) | 6, 8 and 9 Years (+ 45 days) ¹¹ |
| Informed Consent | X | | | | | | | |
| History & Physical | X | | | | | | | |
| Medications ¹ | X | X | X | X | X | X | X | X |
| NYHA Functional Class | X | | | X | X | X | X | |
| SF-36 Health Survey | X | | | X | | X | | |
| 12-lead ECG | X | | X | X | X | | | |
| TTE | X ² | | X | X | X | X | X | |
| Gated CTA | X ³ | | X ⁷ | | | | X ⁹ | |
| cMRI | X ⁴ | | | | | X | | |
| CXR ⁸ | | | X | X | | | X ¹⁰ | |
| Fluoroscopy | | | | | X | X | X ¹⁰ | |
| WBC, Hgb, Hct, Platelets | X | | | | | | | |
| Serum Creatinine | X | | | | | | | |
| Pregnancy test ⁵ | X | | | | | | | |
| INR, if taking Warfarin | X | | | | | | | |
| Case Review | X | | | | | | | |
| Alterra Procedure | | X | | | | | | |
| THV Implant Procedure ⁶ | | X | | | | | | |
| Pre- and Post-implantation Assessments | | X | | | | | | |
| Adverse Event Assessment | | X | X | X | X | X | X | X |

1. Antithrombotics, antiarrhythmics, heart failure medications and antibiotics only
2. Must be performed within 90 days prior to the Alterra implant procedure
3. General assessment of RVOT/PV, pulmonary artery and right heart anatomic parameters. Must be performed within 1 year prior to the Alterra implant procedure and meet the defined parameters within the applicable Core Lab Manual of Operations.
4. General assessment of RVOT/PV and right heart function. Must be performed within 1 year prior to the Alterra implant procedure and meet the defined parameters within the applicable Core Lab Manual of Operations.
5. If female of childbearing potential only (either urine or serum are acceptable)
6. This may be done in a two-stage approach
7. Must be performed after the valve implant procedure but prior to the end of the 30 days follow up period
8. If CXR reveals potential device fracture, fluoroscopy should be completed for confirmation. If another radiographic assessment (CT, fluoroscopy) has been performed by which fracture can be assessed, then CXR does not need to be performed.
9. At years 5 and 10 only
10. CXR or fluoroscopy. For subjects with a previously identified device fracture, fluoroscopy must be performed.
11. Telephone or office visit

7.8 Missed Visits / Subject Discontinuation

7.8.1 Missed Visits

Site personnel should make all reasonable efforts to locate and communicate with the subject at each visit time point. For each missed visit, multiple attempts to contact the subject should be made and details recorded in source documentation

7.8.2 Subject Discontinuation

Every subject should remain in the study until completion of the required follow-up period; however, a subject's participation may be discontinued. Should this occur, the reason for discontinuation should be documented in the subject's medical record. Potential reasons for discontinuation may include, but are not limited to the following:

- Subject Withdrawal: Subject participation in a clinical trial is voluntary and the subject may discontinue participation (refuse all subsequent testing/follow-up) at any time without loss of benefits or penalty.
- Investigator Termination: The investigator may terminate the subject's participation without regard to the subject's consent if the investigator believes it is medically necessary
- Investigational Device Never Implanted: Subjects considered enrolled but the Alterra Adaptive PreStent was never implanted will be followed for 30 days or until resolution of any adverse events related to the study implant procedure, whichever is later, and then exited from the study.
- Investigational Device Explanted: Subjects who have the study valve explanted (e.g., valve replaced due to endocarditis or subject growth requiring larger valve) will be followed for 30 days post-explant or until resolution of any adverse events related to the procedure, whichever is later, and then exited from the study.
- Lost-to-Follow-up: A subject is not considered lost-to-follow up until the full 10 years of follow-up have elapsed.

Subjects that have valvuloplasty or valve-in-valve procedure will continue to be followed for the duration of the study.

Subjects who discontinue prematurely will be included in the analysis of results and will not be replaced.

For subjects that are lost-to-follow-up or withdraw early, Edwards may request the site to search the Social Security Death Index and/or other death registries and may request the site to obtain the death certificate, if applicable.

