5.3 Additional Safety and Effectiveness Outcomes

The following additional outcomes will be evaluated:

Main Cohort:

- Improvement in tricuspid regurgitation (TR) from baseline to 30 days and 6 months by TTE for subjects with TR of mild or greater at baseline
- Major vascular complications at 30 days and 6 months
- Life-threatening or disabling bleeding at 30 days and 6 months
- Alterra embolization at 30 days and 6 months
- THV embolization at 30 days and 6 months
- Alterra fracture that led to reintervention at 30 days and 6 months
- THV frame fracture that led to reintervention at 30 days and 6 months
- All-cause mortality at 30 days and 6 months
- Acute Device Success, defined as a non-hierarchical composite of:
 - Single Alterra deployed in the desired location
 - Single THV implanted in the desired location within Alterra (staged procedures allowed)
 - RV-PA peak-to-peak gradient < 35 mmHg post-THV implantation
 - Less than moderate total PR by discharge TTE (or earliest evaluable TTE)
 - Free of Alterra explant at 24 hours post-implantation

PDS Registry:

- Improvement in tricuspid regurgitation (TR) from baseline to 30 days by TTE for subjects with TR of mild or greater at baseline
- Major vascular complications at 30 days
- Life-threatening or disabling bleeding at 30 days
- Alterra embolization at 30 days
- THV embolization at 30 days

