10.6 Additional Safety and Effectiveness Outcomes

All clinically relevant baseline and follow-up variables will be tabulated. Descriptive statistics will be used for continuous variables (e.g., mean, standard deviation, sample size, minimum, and maximum) and frequency tables or proportions for discrete variables. Kaplan-Meier (KM) estimates will be performed at the pre-specified follow-up times to project the estimates for time-related safety endpoints.

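### Vital status to day 180 is not collected for subjects who exit after valve explant or without an Alterra, so 6-month all-cause mortality may be understated

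*Combined protocol and SAP*

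**What the plan says.** Section 5.3 lists "All-cause mortality at 30 days and 6 months" among the additional outcomes for the main cohort. Section 10.6 plans Kaplan-Meier estimates "to project the estimates for time-related safety endpoints" and names no analysis population. Section 7.5 counts visits from the valve implant and sets six months at 180 days.

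Section 7.8.2 sets the exit rules:

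- Subjects whose study valve is explanted "will be followed for 30 days post-explant or until resolution of any adverse events related to the procedure, whichever is later, and then exited". The two examples given are endocarditis and growth that calls for a larger valve.
- For subjects without the prestent: "Subjects considered enrolled but the Alterra Adaptive PreStent was never implanted will be followed for 30 days", or until procedure-related events resolve if that is later, and they then leave the study.
- Subjects who have valvuloplasty or a valve-in-valve procedure stay in follow-up throughout.
- Subject withdrawal is a separate entry, in which "the subject may discontinue participation (refuse all subsequent testing/follow-up) at any time without loss of benefits or penalty".
- On loss to follow-up: "A subject is not considered lost-to-follow up until the full 10 years of follow-up have elapsed".
- On tracing: "For subjects that are lost-to-follow-up or withdraw early, Edwards may request the site to search the Social Security Death Index" or other death registries.
- On analysis: "Subjects who discontinue prematurely will be included in the analysis of results and will not be replaced".

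Section 8.2 captures adverse events only until participation ends. Section 8.1 records death only as the outcome of another adverse event.

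**The concern.** Kaplan-Meier assumes that subjects who are censored have the same later risk as those who remain under observation. Here some censoring would be triggered by explant. At least one of the protocol's own reasons for explant, endocarditis, is plausibly linked to the risk of death. The rule is also selective, because subjects with less radical reinterventions are kept and subjects with explants are released.

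Once a subject has exited, no adverse-event reporting, scheduled contact or required vital-status check would reveal a death before day 180. The statement that discontinued subjects are included in the analysis does not say how their status after exit is found or handled.

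At stake is the credibility of a low or zero 6-month mortality figure in a study of at most 60 main-cohort subjects. If any bias arises from deaths missed after explant, it makes the device look safer.

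**Working it through.** **The plan's own figure.** The only computed figure is the primary-endpoint power in section 10.1, which does not concern mortality. With n = 38, the goal is met if at most 4 subjects have THV dysfunction: 4/38 has an exact 95% upper limit of 24.8%, and 5/38 has 28.1%.

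- Alpha = P(X ≤ 4 | n = 38, p = 0.25) = 0.0235, as stated.
- Power = P(X ≤ 4 | n = 38, p = 0.074) = 0.8531, as stated.

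Neither figure depends on what follows.

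**When an exit precedes 6 months.** Let t be the day of explant, counted from valve implant. Exit is at the later of t + 30 and resolution of procedure-related events. Exit before day 180 requires t + 30 < 180, so t < 150, with those events resolved. Later explants, and earlier ones with unresolved events, are still under observation at day 180. Subjects who never received a valve have no day 0 under section 7.5, so their 6-month point is undefined.

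**Inputs for size.** N = 60 is the maximum main-cohort enrolment (section 10.1). The documents give no explant rate and no mortality rate. The number of exits before day 180 (k) and the risk of death between exit and day 180 (q) are therefore assumptions, shown as ranges. Intervals are exact binomial 95%.

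**No deaths observed.** Kaplan-Meier gives 0% whatever k is. The upper limit for 0/60 is 6.0%. The worst case, in which every early exit dies unseen before day 180, is k/60:

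| k | Worst case | Exact 95% upper limit |
|---|---|---|
| 1 | 1/60 = 1.7% | 8.9% |
| 2 | 2/60 = 3.3% | 11.5% |
| 3 | 3/60 = 5.0% | 13.9% |

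For k = 1 the full interval is 0.04% to 8.9%.

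**One death observed after the exits.** Kaplan-Meier gives 1/(60 − k); the worst case is (1 + k)/60.

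| k | Kaplan-Meier | Worst case |
|---|---|---|
| 1 | 1/59 = 1.69% | 2/60 = 3.3% |
| 2 | 1/58 = 1.72% | 3/60 = 5.0% |
| 3 | 1/57 = 1.75% | 4/60 = 6.7% |

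**Expected understatement.** With no observed deaths it is 100 × q × k/60 percentage points. For q from 5% to 30%:

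- k = 1: 100 × 0.05 × 1/60 = 0.08 to 100 × 0.30 × 1/60 = 0.5 points.
- k = 3: 100 × 0.05 × 3/60 = 0.25 to 100 × 0.30 × 3/60 = 1.5 points.

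**The case against.** A reader might infer that registry tracing has to wait until year 10, because lost-to-follow-up status cannot be given sooner. The text does not support that. Early withdrawal is a separate trigger in the same sentence and involves no wait. The ten-year rule also works against premature censoring: a subject who misses the 6-month visit stays in the study, section 7.8.1 requires multiple contact attempts for each missed visit, and section 7.5 schedules yearly contact to year 10. A death before day 180 can thus be learned later and dated correctly.

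A reader might also infer that the mortality estimate is certainly biased. That is not shown either:

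- Thirty days is a minimum, and deaths within it, or while a procedure-related event is unresolved, are captured.
- One of the two explant examples, growth, does not suggest high mortality.
- It is not established that never-implanted subjects enter the 6-month estimate, since section 10.6 names no population.
- The illustration assumes the unseen death, and the intervals for 0/60 and 1/60 overlap widely.

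Finally, mortality carries no performance goal or test, and Appendix B counts surgical valve replacement as reintervention for the primary endpoint.

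All of this stands, and it narrows the point. What remains is that explant and never-implanted exits are listed apart from subject withdrawal, so the tracing sentence does not expressly cover them, and that tracing is discretionary in any case. Counting an explant as a reintervention does not show whether the subject was alive at day 180.

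**Conclusion.** The plan has a real but small gap. Followed as written, it can lose sight of subjects before day 180 after an early explant, and of subjects never implanted, without collecting their vital status. The 6-month all-cause mortality estimate may therefore be informatively censored in the device's favour. This reading takes mortality to be one of the time-related safety endpoints of section 10.6.

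Each such exit leaves up to 1/60 = 1.7 percentage points of mortality unobserved. The expected understatement is well under that unless exits are several and the risk after exit is high. Whether any bias occurs depends on the number of early exits and their later risk, which the documents do not give. Primary-endpoint power, alpha and decision rule are unchanged. This is a cheap improvement to a descriptive safety figure and does not threaten the trial's main conclusion.

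**What to change.** - **Section 7.8.2, vital status:** obtain day-180 vital status, by telephone or record check, for every enrolled subject who exits early and has not withdrawn consent. Count from the Alterra procedure for subjects without a valve implant.
- **Section 7.8.2, tracing:** extend the optional registry search to all early exits and to subjects who miss the 6-month visit.
- **Section 10.6:** estimate 6-month all-cause mortality in the All Treated population using this vital status. Add a worst-case sensitivity analysis that counts any subject of unknown status as dead.

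The cost is one contact for what should be a handful of subjects, a line in the consent form, and a mortality figure that may be slightly less favourable.

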8 ADVERSE EVENTS

8.1 Adverse Event Definitions

An Adverse Event (AE) is any untoward medical occurrence, unintended disease or injury or untoward clinical signs (including abnormal laboratory findings) in subjects, users or other persons, whether or not related to the investigational medical device.

AEs may be volunteered by subjects, elicited by the Investigator or designee, the Clinical Events Committee (CEC), safety team, monitoring team, or collected via observation by the Investigator. In addition, subjects should be instructed to contact the investigator, and/or study coordinator if any significant AEs occur between study visits.

All AEs will be assessed by the Investigator who will determine whether or not the event is related to the device and/or implant procedure and if it meets serious criteria. If it is determined that an AE has occurred, the investigator should obtain all the information required to complete the AE electronic Case Report Form (eCRF).

A Serious Adverse Event (SAE) is any AE that:

- led to death
- led to a serious deterioration in the health of the subject, that either resulted in:
 - a life-threatening illness or injury
 - a permanent impairment of a body structure or a body function
 - in-patient or prolonged hospitalization, or
 - medical or surgical intervention to prevent life threatening illness or injury or permanent impairment to a body structure or a body function
- led to fetal distress, fetal death or a congenital abnormality or birth defect
- Important medical event: Important medical events that do not meet the above criteria may still be considered an SAE if they seriously jeopardize the subject and require immediate medical or surgical intervention to prevent one of the aforementioned outcomes.

An Unanticipated Adverse Device Effect (UADE) is any serious adverse effect on health or safety or any life-threatening problem or death caused by, or associated with a device, if that effect, problem, or death was not previously identified in nature, severity, or degree of incidence in the investigational plan or application (including a supplementary plan or application), or any other unanticipated serious problem associated with a device that relates to the rights, safety or welfare of subjects.

Pre-existing medical conditions or symptoms reported prior to subject enrollment will not be recorded as an AE. In the event there is a worsening in the pre-existing medical condition due to the device or study related procedure, then an AE must be recorded.

Death should not be recorded as an AE, but should only be reflected as an outcome to another specific AE.

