8.2 AE Reporting Requirements

All AEs will be captured from the time of enrollment until subject participation has ended (i.e. completion of study or subject discontinuation). AEs must be followed until resolution, stabilization or study completion. Expected, non-clinically significant events such as non-significant lab variances are not required to be reported.

AE information must be entered into the EDC. When EDC system is not available/accessible, AE information must be reported directly via email to [contact], copying the Safety Officer of the study.

At the time of initial notification, the following minimal information must be provided:

- Study site
- Subject ID
- AE description
- Causal relationship to device and implant procedure
- Aware date

The site Principal Investigator is responsible for informing the IRB/EC of SAEs, UADE and/or AEs, as required. A copy of this report should be provided to Edwards Lifesciences (or designee).

Enrolling sites must provide to the Sponsor at a minimum an index hospitalization admission history and physical, implant procedure report, discharge summary, and relevant echocardiographic reports for all enrolled subjects. This will be done irrespective of subject having any AE/SAE.

The site will provide a copy of supporting documentation (example: admission H&P, index procedure reports, anesthesia records, discharge summary, echocardiogram and ECG reports, laboratory results, etc.) for all endpoint-related events, device and procedure-related events, and UADEs to Edwards Lifesciences (or designee). Source documentation may be requested by the Edwards Safety Officer for other AEs that may meet potential complaint reporting criteria or in order to verify that events are being assessed appropriately.

All AEs must be reported to Edwards Lifesciences **within 10 working days of the site becoming aware of the event.**

Edwards Lifesciences will notify FDA, all participating investigators and participating IRBs/ECs of all UADEs that occur during this study within 10 working days of the Sponsor becoming aware of the event. Investigators are responsible for reviewing information received about UADEs.

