8.3 Investigator Assessment

For each AE, the investigator will determine whether the event is related to the device and/or the procedure, and whether the event meets the definition of a SAE or UADE as outlined in **Section 8.1**.

The causal relationship of the event to the device and the procedure will be categorized as follows:

- **None:** The event is not associated with the device or procedure. There is no relation between the event and the device or procedure.
- **Possibly Related:** The temporal sequence between the device or procedure and the event is such that the relationship is not unlikely or there is no contradicting evidence that can reasonably explain the study subject's condition. There is a possibility of any relation between the event and the device or procedure.
- **Definitely Related:** The temporal sequence is relevant or the event abates upon device application completion/removal or the event cannot be reasonably explained by the subject's condition or comorbidities. The event is related or most likely associated with the device or procedure.

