8.4 Sponsor Assessment

All AEs will be reviewed by the Edwards Safety Officer. Each AE will be assessed as to its relationship to the study device and/or procedure, whether it was anticipated or not anticipated, based on the list of anticipated events provided in **Section 9.2**, and whether it qualifies as an SAE and/or UADE.

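### Section 8.1 ties the duty to record worsening of a pre-existing condition to device or procedure causality, in conflict with the protocol's own AE definition and capture rule

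*Combined protocol and SAP*

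**What the plan says.** Section 8.1 defines an AE as any untoward occurrence, "whether or not related to the investigational medical device". Later in the same section come two sentences on medical history. The first is an exclusion: "Pre-existing medical conditions or symptoms reported prior to subject enrollment will not be recorded as an AE". The second is the exception, which applies in the event of a "worsening in the pre-existing medical condition due to the device or study related procedure, then an AE must be recorded". Nothing is said about a worsening that is not due to the device or procedure, or whose cause is uncertain.

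The surrounding sections carry no causality condition on recording. Section 8.2 states: "All AEs will be captured from the time of enrollment until subject participation has ended". Section 8.3 places attribution after recording: "For each AE, the investigator will determine whether the event is related to the device and/or the procedure". One of its three grades, *None*, is described as "The event is not associated with the device or procedure". Section 8.4 adds a second look by the sponsor: "All AEs will be reviewed by the Edwards Safety Officer", and "Each AE will be assessed as to its relationship to the study device and/or procedure".

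**The concern.** The general scheme is to record first and attribute afterwards. For one class of event the specific rule reverses that order: the site must decide on cause before it knows whether an AE record is required. A worsening that the site attributes to natural history then has a textual basis for not being entered, and there may be nothing for others to re-assess.

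The class of event matters here. Section 1.1 associates chronic pulmonary regurgitation with arrhythmia, reduced ventricular function and right heart failure. Section 9.2 lists arrhythmia, conduction system injury, cardiac failure and tricuspid valve injury among the risks of the procedure or devices. The conditions that subjects may bring into the study are therefore also ones the intervention might aggravate. The study has a single arm, so no control rate would show that worsening was being under-recorded or that sites were attributing it unevenly. Under Section 8.1 an effect can also count as unanticipated because of its degree of incidence, which is hard to judge from counts already filtered by cause.

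**Working it through.** No figure in the plan bears on this point, so nothing was computed. The check sets the provisions side by side.

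| Provision | Does recording depend on cause? |
|---|---|
| AE definition (8.1) | No |
| Pre-existing conditions (8.1) | Excluded from recording |
| Worsening of a pre-existing condition (8.1) | Duty stated only for worsening caused by device or procedure |
| Capture rule (8.2) | No |
| Causality grades (8.3) | No; *None* and *Possibly Related* presuppose a recorded event |

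**Step 1: what happens to a worsening judged unrelated.** The general definition and the capture rule say to record it. The exclusion sentence, with its single stated exception, suggests not. The two readings lead to different records for the same event.

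**Step 2: what happens to a worsening that is possibly related.** The exception requires that the worsening be due to the device or procedure. The *Possibly Related* grade in 8.3 is looser: it is enough that a relationship is not unlikely, or that no contradicting evidence explains the subject's condition. An event that 8.3 would grade *Possibly Related* can thus fail the test in 8.1 and never be graded. For a pre-existing condition the natural course of the disease is often an available explanation, so doubtful cases lean toward no record.

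**Step 3: who would see an unrecorded event.**
- The Safety Officer's review in 8.4 works on AEs. An event with no record receives no second view on relatedness.
- The DSMB (11.4) evaluates trends in reported AEs.
- The Clinical Events Committee (CEC, 11.5) adjudicates endpoint events, and AEs that the site or the Safety Officer has called related. An unrecorded worsening that is not an endpoint event does not reach it by that route.

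**Step 4: which analyses are exposed.** The primary endpoint (10.3) rests on reintervention and on regurgitation and gradient by transthoracic echocardiography (TTE). The labeling endpoint (10.5.1) is change in regurgitation grade. Echo images go to an independent core lab (11.6.3). None of the additional outcomes in 5.3 is worsening of a pre-existing condition as reported through the AE form; change in tricuspid regurgitation is taken from TTE. What remains exposed is the AE and serious AE tabulations.

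**The case against.** The strongest reply is that the sentence does not say *only if*. It can be read as a minimum duty inside a broader one, since the general definition and the capture rule still stand, and a serious decline in health falls within the serious AE definition. This is right as far as it goes: the text is not a ban, and a site may record an unrelated worsening. But the sentence directly follows an exclusion and is its only stated exception, so not recording is a natural reading, and sites may differ.

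A reader might go further and infer that such events never reach the Safety Officer, the CEC or the DSMB, or that AE reporting is the only protection. The documents do not support that:
- The CEC, safety team and monitoring team may themselves elicit AEs (8.1).
- Index hospitalization, procedure, discharge and echo documents go to the sponsor for every subject (8.2).
- Monitors compare case report forms with medical records (11.9).
- The DSMB reviews study data as well as AE trends (11.4).
- Scheduled data are collected whatever the site thinks of cause: ECG through 6 months, the listed medications at every visit, NYHA class and TTE at most visits, and cardiac MRI at 12 months (7.4, 7.5, Table 3).

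These routes soften the problem but do not remove it. Monitors check compliance with a protocol that can be read as permitting the omission. No ECG is scheduled after 6 months, and years 6, 8 and 9 collect only medications and AEs.

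It is also fair to say that the fix does not by itself bring independent adjudication. An event recorded as unrelated goes to the CEC only if it is an endpoint event or the Safety Officer calls it related.

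**Conclusion.** The point stands as an internal contradiction that should be corrected. As written, Section 8.1 lets a site leave out a worsening it judges unrelated or only possibly related, against the definition in 8.1, the capture rule in 8.2 and the grades in 8.3. The consequence is a risk of selective and inconsistent recording in the AE and serious AE tabulations of a single-arm study.

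The conclusion rests on reading the exception together with the exclusion before it, and assumes that at least some sites would follow that reading. The size cannot be derived: the documents do not say how many subjects enter with arrhythmia or heart failure, how often these worsen, or how sites would attribute the worsening. A reader might infer that the primary or labeling result is at risk. It is not, because those endpoints rest on echo measurements and reintervention and not on AE recording of worsening.

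**What to change.** Replace the sentence on worsening in Section 8.1 with:

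> Any clinically significant worsening of a pre-existing condition from its baseline state after enrollment, whether or not related to the device or procedure, will be recorded as an AE, with relatedness assessed separately under 8.3 and 8.4.

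The clinical-significance limit keeps the sentence in line with Section 8.2, which already exempts expected events without clinical significance. The same wording should go into the case report form guidance. No endpoint, analysis or clinical management changes. The cost is some additional AE forms over the 10-year follow-up and slightly higher reported AE counts; how many more cannot be estimated from the documents.
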